## 4.3 Handling of Missing Data

Missing data will not be imputed; the statistical analyses will be based on cases with relevant data available. For endpoint calculations, if missing data makes it so a case (subject or a dosing instance) cannot be classified as to whether or not it belongs in the numerator, that case will also be excluded from the denominator. All missing data will be flagged, and a reason for why the data are missing will be described in a footnote in each applicable statistical table.

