6.4 Pregnancy Testing

During the enrollment interview, after answering the self-selection question, all subjects will be asked if they are currently pregnant, and after informed consent is obtained, subjects will perform a self-administered pregnancy test at the site. Subjects with a positive result will be asked the selection question again, and then excluded from participating in the use phase of the study. Additionally, at the end of the enrollment interview, subjects who are proceeding into the use phase will be provided with a home pregnancy test with the instructions to use it at home at the end of the study and record the results in the online diary. Nurse interviewers will inquire about the results of the home pregnancy test during the EOS interview. After completion of the EOS interview, subjects will be asked to return to the study site to return all unused study medication and packaging. During that visit, an additional pregnancy test will be administered and results entered by site staff. If subjects have not completed the home pregnancy test at the EOS interview, and if they have not returned to the study site for the site-recorded pregnancy test, an additional call will be placed at 5 (+3) days following the EOS interview to collect home pregnancy test results. This will allow for shipping time if the subject requires an additional at home pregnancy test to be sent to them. In addition, at the time a subject withdraws or is withdrawn from the study early, nurse interviewers will inquire if the subject would be willing to take the pregnancy test and report the results in their electronic diary and return to the site for the EOS visit.

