9.3.3.6 Actual Use: Number of pregnancies reported during the course of the study

This endpoint is intended to characterize the pregnancies that may occur during the course of the study. While it does not directly measure behavior related to messages on the DFL, it is of interest. For the purposes of this endpoint, pregnancies will be defined as any reported pregnancy during the use phase of the study, or any confirmed positive pregnancy test (at home or at EOS visit) that is conducted within 12 days of the end of the subject's use phase.

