All users had a unique login user name and password, and system access privileges were strictly controlled and documented. Whenever data was modified after the initial data entry process, a computer-generated audit trail entry was created. The audit trail, user access privilege processes, and electronic signatures collected by the system were compliant with 21 CFR Part 11 requirements.

A web-based electronic diary was provided to all subjects with a reliable internet connection. The e-diary was programmed and hosted by a qualified vendor

(eClinicalHealth Ltd, Stirling, United Kingdom). Subjects were instructed to record information regarding their use of the study product every day. Subjects were also asked to enter additional data regarding sexual behaviors (heterosexual vaginal intercourse) and additional contraception methods to fully evaluate adherence to label directions. The electronic diary was intended to serve as the primary means of reporting the results of the EOS at-home self-administered pregnancy test. Diary data were imported into the EDC system to be included in the study database.

However, as noted previously, problems with the usability and reliability of the e-diary system led to the premature termination of this study.

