## 5. Analysis Sets

The populations of interest are defined as follows:

- Screening Population: All those who respond to study advertisements and begin initial screening questions.
- Self-Selection Population: Participants who accept the invitation to participate and meet study inclusion criteria, participate in a face-to-face interview at the study site, make a self-selection decision, and provide responses to all relevant medical history questions.
- Safety Population: Subjects who signed the informed consent document.
- Purchasers: Responders who meet study enrollment criteria and purchase/obtain the study medication.
- User Population: Subjects who take at least one dose of study medication during the study.

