## 6. Statistical Methodology

This is a naturalistic, observational trial to assess selection and use patterns from the prospective OTC population in a simulated OTC setting. The analyses will largely employ descriptive statistics including frequencies, percentages and appropriate summary statistics.

Tabulations of frequencies for categorical data will include all possible categories and will display the number of observations in a category as well as the percentage (%) relative to the respective subject set. Percentages will be rounded to one decimal place. The category of missing data will be displayed only if there are actually missing values.

Each of the categorical endpoints will be evaluated by computing point estimates and their binomial two-sided 95% confidence intervals (CIs) (calculated using the exact Clopper-Pearson method).

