## 6.2.2 Secondary Endpoint Analysis

Only Secondary Endpoint F will be analyzed and reported on for this study: Actual Use: Number of pregnancies reported during the course of the study

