#### 6.2.4.2 Pregnancies

All pregnancies that were reported during the study will be described including an assessment of whether they occurred on or off the study drug.

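### Does the pregnancy endpoint need a stated denominator and a rule for women with no end-of-study test?

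*SAP*

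**What the plan says.** The study stopped early because of technical problems with the e-diary (SAP 1). Of the secondary endpoints, SAP 6.2.2 keeps one: "Only Secondary Endpoint F will be analyzed and reported on for this study". SAP 6.2.4.2 then states "All pregnancies that were reported during the study will be described", with an assessment of whether each occurred on or off study drug.

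The definition is in Protocol 9.3.3.6. It counts a pregnancy reported during the use phase, or "any confirmed positive pregnancy test (at home or at EOS visit) that is conducted within 12 days of the end" of the use phase.

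Four pieces of general text could bear on this endpoint:

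- SAP 4.3: nothing is imputed, and if missing data mean a case "cannot be classified as to whether or not it belongs in the numerator, that case will also be excluded from the denominator". Missing data are flagged and the reason footnoted in each table concerned.
- SAP 6: "Each of the categorical endpoints will be evaluated by computing point estimates and their binomial two-sided 95% confidence intervals", with percentages taken relative to the relevant subject set. Protocol 9.3 similarly asks for percentages and exact intervals for the secondary endpoints.
- SAP 5: the Safety Population is "Subjects who signed the informed consent document"; the User Population is everyone who took at least one dose. Neither is assigned to Endpoint F.
- Protocol 6.4: "after informed consent is obtained, subjects will perform a self-administered pregnancy test at the site", so the enrollment test comes after consent and before product is dispensed.

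**The concern.** Pregnancies are one of only two outcomes still reported, and the SAP names no set of women for them. Two things then look open.

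The first is the untested woman. If she has no end-of-study test and has reported no pregnancy, SAP 4.3 can be read as removing her because her status is unknown. She can equally be read as a woman with no reported pregnancy, who stays in. A woman who reports a pregnancy is always classifiable, so exclusion could only remove women from the non-pregnant side and raise the proportion. Missing tests are plausible, because SAP 4.6 says "The electronic diary was intended to serve as the primary means of reporting the results of the EOS at-home self-administered pregnancy test", and that diary is what failed.

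The second is the population. Pregnancy is handled as a safety outcome, and the Safety Population starts at consent. It therefore includes women whose enrollment test was positive before they received any product. If they were counted, the result would describe something other than pregnancies during use.

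At stake is whether two analysts with the same data could publish different percentages and upper limits, and whether a bare count of 0 or 2 could be interpreted without knowing how many women had their status established.

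**Working it through.** **1. Does the count depend on the reading?** Apply Protocol 9.3.3.6 to each kind of woman.

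| Woman | In the count? | In a denominator? |
|---|---|---|
| Pregnancy reported in the use phase | Yes, both readings | Yes, both |
| Confirmed positive within 12 days after it | Yes, both | Yes, both |
| Negative end-of-study test, no reported pregnancy | No, both | Yes, both |
| No test and no reported pregnancy | No, both | Differs |
| Positive at enrollment | No: kept out of the use phase (Protocol 3.3.2, 6.4) | Not a user |
| First positive after the 12-day limit | No | Described under SAP 6.2.4.2, outside Endpoint F |

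The two readings of SAP 4.3 differ in one cell only, and only if a denominator is used.

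**2. Is a denominator part of the endpoint?** Secondary endpoints A to E in Protocol 2.2.2 are each worded as a proportion. F alone is worded as a number. The specific text, SAP 6.2.4.2, promises case descriptions and no percentage. The request for percentages comes only from the general sentences in Protocol 9.3, SAP 4.1 and SAP 6.

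**3. Check of the interval method.** The exact 95% limits for x events in n are the 0.025 quantile of Beta(x, n − x + 1) and the 0.975 quantile of Beta(x + 1, n − x). The plan states ±2.8% around 85% at N = 720. With x = 612 the distance from 85% to the lower limit is 2.82 points, which reproduces it. The distances at N = 900, 576 and 135 are 2.50, 3.18 and 7.16 points, matching the stated 2.5, 3.2 and 7.2. The plan gives no figure for pregnancies.

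**4. Size if a percentage is reported.** Let N be users, x pregnancies and m the share excluded as untested. The ratio of the two percentages is [x / (N(1 − m))] / (x / N) = 1/(1 − m): 1.11 at m = 10%, 1.25 at 20%, 1.67 at 40%. N, x and m after termination are not in the documents. The rows for 100 and 50 users are assumed; the 720 row uses the planned users and the planned 20% loss (720 × 0.80 = 576), with 6 pregnancies assumed.

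| Users, pregnancies | All users | Untested excluded |
|---|---|---|
| 100, 2 | 2.0% (0.2 to 7.0) | n = 90: 2.2% (0.3 to 7.8); n = 80: 2.5% (0.3 to 8.7); n = 60: 3.3% (0.4 to 11.5) |
| 100, 0 | upper limit 3.6% | n = 90: 4.0%; n = 80: 4.5%; n = 60: 6.0% |
| 50, 0 | upper limit 7.1% | n = 45: 7.9%; n = 40: 8.8%; n = 30: 11.6% |
| 720, 6 | 0.83% (0.31 to 1.80) | n = 576: 1.04% (0.38 to 2.25) |

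The intervals overlap heavily in every row that has events.

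**5. Does a failed diary mean unknown status?** The diary is the main route for the home test result only. The end-of-study interview asks about possible pregnancy and a telephone contact can collect the home result (Protocol 5.4.3.2). An extra call is placed at 5 (+3) days if neither test is done (6.4). The site visit test is confirmed and recorded by staff (5.4.4). None of these needs the diary, so a woman with no diary entry need not be unclassifiable.

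**6. The population example.** One use-phase pregnancy in 100 users is 1.0%. Adding two enrollment positives over 125 consented women gives 3/125 = 2.4%. The 125 is 100/0.80, but that 80% is the plan's ratio of users to purchasers, not to consented women, and the two enrollment positives are assumed. The example also needs an analyst to set aside Protocol 9.3.3.6 and adopt a population the SAP does not assign to this endpoint.

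**The case for a change.** The best case for a change is this. Protocol 9.3 asks for percentages and exact intervals for the secondary endpoints, SAP 4.1 and SAP 6 repeat the request, and nothing exempts F. Other Measure A names the user population while F names no population. SAP 5 introduces a Safety Population that Protocol 9.2 does not have. The wording of SAP 6.2.4.2 is wider than Protocol 9.3.3.6: enrollment positives, and positives at late visits (accepted until the study ends under Protocol 5.4.4 and 6.8), fit the former and not the latter. A few sentences before database lock would remove the doubt.

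What stands is that no analysis set is named and that the general sentences can be read as asking for a percentage. What does not follow is that the result is at risk. A description may cover more cases than a count; F carries an Actual Use label and a protocol definition that the SAP nowhere replaces. SAP 4.1 shows a missing category where values are missing, SAP 4.2 puts withdrawn and lost women in the disposition table, and SAP 4.3 footnotes missing data, so the count would not stand bare.

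Adding a second proportion among women with established status is not a clear gain either. If status counts as established by a pregnancy reported at interview but not by a denial at interview, the exclusion falls only on the non-pregnant side, which is the very bias the concern raises. Keeping untested women in can understate the rate. No denominator repairs a missing test; showing the numbers is what helps.

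**Conclusion.** No change is needed. The SAP leaves out a detail, and analysts would fill it sensibly: the number of pregnancies among users as Protocol 9.3.3.6 defines them, shown with the number of users and the number with no test or interview information, and with any other reported pregnancies described separately.

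The count does not move between the readings. A derived percentage would move by 1/(1 − m): about a tenth at 10% untested, a quarter at the planned 20%, two thirds at 40%. Those shares, the illustrative 50 and 100 users and the event counts are assumptions; if nearly all users were tested, the difference all but disappears. SAP 4.3 does lean towards exclusion, so a percentage under either reading should be labelled with its denominator, as good reporting requires anyway.

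No decision rests on the figure. There is no threshold for pregnancies, Protocol 2.3 says no efficacy conclusion can be drawn, all SAP analyses are descriptive, and SAP 1 calls the sample too small for the planned endpoint analyses.

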#### 4.4 Handling Protocol Violations

All deviations from the protocol will be reviewed and any decision regarding inclusion or exclusion of subjects in study analyses due to the presence of a deviation will be made and documented before database lock.

Events that qualify as protocol deviations will be identified in a separate document. All protocol deviations will be categorized and assessed to determine the severity of the deviation and reviewed before database lock.

A full list of protocol deviations will be included in the final Clinical Study Report (CSR).

# 4.5 Interim Analyses and Data Monitoring

No interim analyses are planned for this study. Final data analyses will be performed upon database lock. Data were monitored by site monitors and PEGUS data management staff on an ongoing basis to ensure protocol procedures were being followed. While a formal Independent Data Monitoring Committee was not established for this study, the sponsor was informed of study progress, amount and nature of data queries, and protocol violations.

# 4.6 Data Capture and Processing

Data were collected in structured one-on-one interviews using a standardized questionnaire either in person (at the initial enrollment visit), by telephone (in four follow-up interviews), and in an electronic diary. The interviews were administered by a trained interviewer using an internet-based EDC application in which the interviewer read the introductory scripts and the questions from the screen and entered the responses directly into the study database. The questionnaires included primarily open-ended questions. Question types included direct questions and follow-up questions for clarification. To facilitate the accurate capture of responses, open-ended questions had pre-coded answer alternatives. It is important to note that these response alternatives were not read to the participants, nor were participants able to see them on the screen. Where close-ended questions were used (e.g., yes/no, or ok/not ok), participants were asked to explain their answers so behavior could be adequately assessed. When interviewers recorded open-ended responses, they captured short responses verbatim, and accurately summarized longer responses.

During the self-selection interview at the initial visit, the Opill® outer package including DFL remained in front of the participant and the participant was informed that they could refer to the outer package at any time. However, the participant was neither encouraged nor discouraged from referring to the package in response to any specific question.

Subjects who entered the use phase of the study were asked to use an online diary to record their use of the study product daily. Of note, a device was provided for subjects who did not have easy access to a device with internet access.

Information collected during the participant interviews was entered directly into an EDC application (DATATRAK ONE, DATATRAK International, Inc.). Automatic data checks alerted users of discrepancies and inconsistencies, where applicable. In the event of a data entry error, users had the ability to correct information previously entered. Data Management staff reviewed the information entered as defined in this protocol.

All users had a unique login user name and password, and system access privileges were strictly controlled and documented. Whenever data was modified after the initial data entry process, a computer-generated audit trail entry was created. The audit trail, user access privilege processes, and electronic signatures collected by the system were compliant with 21 CFR Part 11 requirements.

A web-based electronic diary was provided to all subjects with a reliable internet connection. The e-diary was programmed and hosted by a qualified vendor

(eClinicalHealth Ltd, Stirling, United Kingdom). Subjects were instructed to record information regarding their use of the study product every day. Subjects were also asked to enter additional data regarding sexual behaviors (heterosexual vaginal intercourse) and additional contraception methods to fully evaluate adherence to label directions. The electronic diary was intended to serve as the primary means of reporting the results of the EOS at-home self-administered pregnancy test. Diary data were imported into the EDC system to be included in the study database.

However, as noted previously, problems with the usability and reliability of the e-diary system led to the premature termination of this study.

# 4.7 Data Review

Data review were ongoing during the course of this study. Data were reviewed by PEGUS Research for accuracy, and all validation and documentation will be completed before database lock.

## 5. Analysis Sets

The populations of interest are defined as follows:

- Screening Population: All those who respond to study advertisements and begin initial screening questions.
- Self-Selection Population: Participants who accept the invitation to participate and meet study inclusion criteria, participate in a face-to-face interview at the study site, make a self-selection decision, and provide responses to all relevant medical history questions.
- Safety Population: Subjects who signed the informed consent document.
- Purchasers: Responders who meet study enrollment criteria and purchase/obtain the study medication.
- User Population: Subjects who take at least one dose of study medication during the study.

## 6. Statistical Methodology

This is a naturalistic, observational trial to assess selection and use patterns from the prospective OTC population in a simulated OTC setting. The analyses will largely employ descriptive statistics including frequencies, percentages and appropriate summary statistics.

Tabulations of frequencies for categorical data will include all possible categories and will display the number of observations in a category as well as the percentage (%) relative to the respective subject set. Percentages will be rounded to one decimal place. The category of missing data will be displayed only if there are actually missing values.

Each of the categorical endpoints will be evaluated by computing point estimates and their binomial two-sided 95% confidence intervals (CIs) (calculated using the exact Clopper-Pearson method).

# 6.1 Efficacy

Not applicable for this study.

# 6.2 Pharmacokinetics / Pharmacodynamics

Not applicable for this study.

## 6.2.1 Primary Endpoint Analysis

As discussed in Section 2, only endpoints related to safety outcomes will be analyzed and reported on for this study.

## 6.2.2 Secondary Endpoint Analysis

Only Secondary Endpoint F will be analyzed and reported on for this study: Actual Use: Number of pregnancies reported during the course of the study

## 6.2.3 Other Analyses

Only Other Measure A will be analyzed and reported on for this study: Actual Use: Character and frequency of adverse events as reported by the user population

## 6.2.4 Safety and Compliance

#### 6.2.4.1 Adverse Events and Serious Adverse Events

Adverse event (AE) and Serious Adverse Event (SAE) analyses will include all events which initially occurred or worsened following treatment. Adverse events will be summarized by the Medical Dictionary for Regulatory Activities (MedDRA) System Organ Class (SOC) and Preferred Term (PT) and classified according to their severity (mild, moderate, or severe) and relationship (related or not related) to study product. For the summary by severity, subjects who have multiple occurrences of the same AE/SAE will be classified according to the worst reported severity of the AE/SAE. Similarly, for the summary by relationship to the study product, the AE/SAE will be classified according to the worst relationship.

#### 6.2.4.2 Pregnancies

All pregnancies that were reported during the study will be described including an assessment of whether they occurred on or off the study drug.

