chose to will then purchase the IP and site study staff will complete the IP accountability form in the EDC system. Subjects will be told they are allowed to return to the study site at any time to purchase/obtain additional study medication. Subjects will subsequently be reimbursed for all purchases, but are not informed of this until the study is completed. Subjects will not be allowed to purchase/obtain more than 8 four-week supply packages during the study period, although this limit will not be communicated to the subjects unless they attempt to purchase/obtain more than that. Any requests for purchase/dispensing of more than the limit will be recorded, as will the reason for such requests.

Subjects will also be informed that interim and end-of-study phone interviews will be conducted at weeks 4, 8, 12, and 16 (with an allowable window of +/- 4 days for interviews at weeks 4 and 8, and +/-5 days for interviews at weeks 12 and 16). Subjects are not required or directed to continue taking the medication for this period. Subjects who have decided to proceed to the use phase of the study will be dispensed the product to use how and when they see fit based only on guidance from labeling.

Subjects will be introduced to and trained to use the online medication use diary. Subjects will also be provided with a subject information card and a self-administered pregnancy test and given instructions to use the test at the end of the study period. Subjects will record the results of the home pregnancy test in the online medication use diary.

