9.3.4 Other Measures Analysis

The other measures are as follows:

- A. Actual Use: Character and frequency of adverse events as reported by the user population.
- B. Actual Use: Patterns of use in the user population, including discontinuation rates and reasons for discontinuation.
- C. Actual Use: Proportion of user population who experience severe vomiting or diarrhea within 4 hours of taking their daily pill who report using a condom or other barrier method of contraception every time they have sex (or abstain from intercourse) for the next 48 hours.
- D. Actual Use: Characterize healthcare seeking behavior among subjects.

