# 1. Introduction

Opill® (norgestrel 0.075 mg) is proposed for an Rx-to-OTC (over-the-counter) switch. This combined Self-Selection (SS) / Actual Use Trial (AUT) was intended to be conducted to demonstrate appropriate consumer selection and use behavior as guided by OTC labeling when using the product in the absence of a physician or other learned intermediary.

Due to technical issues with the e-diary application, the study was terminated shortly after the study was initiated, resulting in a sample size that is statistically insufficient to analyze the Primary and Secondary Endpoints as well as the Other Analyses described in Section 9.3 of the protocol. As such, only analyses relating to subject safety, including the number of pregnancies observed over the course of the study, will be completed for this study.

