## 4.2 Handling of Withdrawn Subjects

For subjects that chose to withdraw at any point during the study, an attempt was made to collect End-of-Study (EOS) information and the reasons for the subject's early termination. Data gathered prior to subject withdrawal and any ongoing data collection will be included in the analysis for completed questions, unless the subject withdrew consent or requested otherwise. Subjects who did not complete the study will be described in a disposition table. Any subjects who withdrew their consent or were determined to be lost to follow-up will be described in the disposition table as well. Withdrawn subjects were not replaced.

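### Does the SAP need a time-on-drug summary and a written rule for the on/off-drug call before it can report pregnancies and adverse events?

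*SAP*

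**What the plan says.** SAP section 1 records that, because of e-diary problems, "the study was terminated shortly after the study was initiated" and that the sample is too small for the planned endpoints, so only safety is reported. SAP 6.2.2 keeps Secondary Endpoint F, the number of pregnancies. SAP 6.2.3 adds: "Only Other Measure A will be analyzed and reported on for this study". That removes Protocol Other Measure B: "Patterns of use in the user population, including discontinuation rates and reasons for discontinuation".

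SAP 6.2.4 is headed "Safety and Compliance" but covers only adverse events, pregnancies and protocol deviations. On pregnancies it says: "All pregnancies that were reported during the study will be described including an assessment of whether they occurred on or off the study drug". It names no dating method, data source or window.

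On exposure, the SAP defines the User Population as "Subjects who take at least one dose of study medication during the study". SAP 4.2 adds: "Subjects who did not complete the study will be described in a disposition table". Under Protocol 5.3.3 the length of use was left to the woman: "Subjects are not required or directed to continue taking the medication for this period".

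Protocol 9.3.3.6 defines Endpoint F. It counts pregnancies reported in the use phase, plus confirmed positive tests up to 12 days after that phase ends.

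**The concern.** Safety is all that is left to report, and safety counts are normally read against exposure. Here exposure varies and is not shown. Use was voluntary, one tablet makes a woman a user, and the study was cut short. A zero or low pregnancy count, or a low adverse event percentage, could mean few events or simply little time on drug. The one protocol measure that describes stopping has been dropped, and a disposition table shows who left the study, not how long anyone took tablets.

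The on/off call looks exposed as well. The scheduled end-of-study tests come after the use phase. If the label followed the test date, a pregnancy conceived during use could be recorded as off drug. The diary, which was the main source of dosing dates, was the part of the study that failed.

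There are two smaller loose ends. SAP 6.2.4.2 refers to all pregnancies reported in the study and does not repeat the 12-day limit. SAP section 5 defines a Safety Population that no listed analysis uses.

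**Working it through.** The SAP states no figure for this point, so there is none to reproduce. The check has four parts.

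**1. How much does duration matter to a bare count?** For a fixed count and number of users, the rate per woman-time varies as 1/(mean weeks of use). Relative to 16 weeks, the ratios at 4, 8, 12 and 16 weeks are 16/4 = 4, 16/8 = 2, 16/12 = 1.33 and 16/16 = 1.

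As an illustration, assume 100 users and one pregnancy (the documents give neither). The proportion is 1.0%, with an exact 95% interval of 0.03% to 5.45%, whatever the duration. Woman-years = 100 × weeks × 7/365.25, and the rates have exact Poisson limits:

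| Mean weeks | Woman-years | Per 100 woman-years (95% CI) |
|---|---|---|
| 2 | 3.83 | 26.1 (0.7 to 145.4) |
| 4 | 7.67 | 13.0 (0.3 to 72.7) |
| 8 | 15.33 | 6.5 (0.2 to 36.3) |
| 16 | 30.66 | 3.3 (0.1 to 18.2) |

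The point estimate moves 8-fold (16/2), so the arithmetic behind the worry is sound.

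**2. Does any retained conclusion use that rate?** One could ask when zero pregnancies would exclude the 9% typical-use failure rate in Protocol 9.3.2.2:

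- The exact upper limit for zero events is −ln(0.025) = 3.689.
- The yearly hazard for 9% is −ln(0.91) = 0.0943.
- Exposure needed is 3.689/0.0943 = 39.1 woman-years.
- That is about 128 women for 16 weeks (39.1 × 365.25/112) or 511 for 4 weeks (39.1 × 365.25/28).
- The full plan would have given 720 × 112/365.25 = 220.8 woman-years.

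This is an efficacy comparison. Protocol Table 1, under Endpoint F, says the study is not powered for efficacy and that no such conclusion can be drawn. SAP 4.1 makes every analysis descriptive. There is one treatment group (Protocol 7.1), so unequal exposure cannot distort a between-arm comparison.

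**3. Did the SAP remove a denominator that existed?** Protocol 9.3.3.6 defines F without woman-time, even for the full 900-purchaser study. Other Measure B concerns patterns of use, stopping rates and reasons. Neither document defines a duration-of-exposure measure, so the missing denominator does not come from the SAP's cut.

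**4. Can the on/off call be made from what is already specified?**

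| Needed | Where it is |
|---|---|
| Event to be placed in time | SAP 6.2.4.2 asks when the pregnancy occurred, not when it was detected |
| Dating of conception | Protocol 7.9: the exposure-during-pregnancy report should give the anticipated delivery date |
| When use ended | Protocol 9.3.1.2: stopping is the moment after which no more tablets are taken |
| Source if the diary is blank | Protocol 9.3.1.2: telephone interview data |

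The last two entries were written for the adherence endpoints, but an analyst would naturally carry them over. The feared mislabelling needs a test-date rule, which SAP 6.2.4.2 does not state.

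On scope, SAP 6.2.2 names the protocol's Endpoint F, so the definition in Protocol 9.3.3.6 comes with it. The wider description in SAP 6.2.4.2 can stand beside that count. A woman excluded for a positive enrolment test never enters the use phase, so she is not counted in F.

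**The case for a change.** The best argument for a change is that it is cheap and is ordinary good practice. A safety report usually shows exposure, and one table and a sentence or two would do it. The SAP still treats database lock as ahead. Interviews, dispensing records and pack returns were already planned. Fixing the on/off basis in advance also avoids a judgement made with the cases in view.

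Part of this stands. A descriptive duration summary would help a reader, and the SAP states no on/off convention. The data are weaker than the argument assumes, though. Dose dates come mainly from the diary whose unreliability ended the study (SAP 4.6). Protocol 5.4.3.1 promises information on how the tablets were taken, not exact last-dose dates. Women could obtain 8 packs, twice what daily use required (Protocol 4.3.2), so packs dispensed and returned cannot date the last tablet. For an unknown share of users, the table would hold ranges or blanks.

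The risk of false reassurance is also limited, because SAP sections 1 and 4.6 both state the early termination and section 1 calls the sample insufficient. A reader is told not to take comfort from a small count.

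**Conclusion.** No change to the plan is needed. The SAP is thin here: it has no time-on-drug summary, no written on/off convention and an unused Safety Population. But it yields a correct pregnancy count and correct adverse event frequencies, and it draws no inference that depends on woman-time. The rate for a given count could differ 8-fold between 2 and 16 weeks of mean use, yet neither document plans such a rate. The on/off assessment is a case-by-case description that the team can complete sensibly from material the protocol already requires. The unused population is a drafting leftover with no effect on results.

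This rests on three assumptions: that the report keeps to description and makes no efficacy claim from the pregnancy count, that it repeats the early termination beside the results, and that on/off status follows when the pregnancy began and not the test date. The documents do not give actual enrolment or exposure, so the size of any effect on how the counts read cannot be stated.
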